8.2.5 Data linkage

Linkage to Medicare Australia will enable capture of information about skin cancer treatments. This data will be used to assess if regular high SPF sunscreen application reduces the incidence of malignant and pre-malignant skin lesions. Data linkage will be sought for the period between enrolment and up to four years post intervention.

8.2.6 Laboratory Assessments

All blood samples will be analysed at the end of the study. Serum 25(OH)D will be measured using a liquid chromatography tandem mass spectroscopy method. It will most likely occur at Metabolomics Australia, University of Western Australia, with whom we have an existing collaboration, although other companies may start to offer the same assay, so we will select appropriately at the time of testing. The assay is certified to the NIST-Ghent University Reference Measurement Procedure.³² Laboratory staff will be blinded to the group assignment; samples will be randomly distributed across batches to avoid systematic differences between study groups or across time points.

9 Safety Assessments and Reporting

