9.6 Laboratory Specimen Preparation, Handling, Storage and Shipment

Each participant will be asked to provide 3 blood samples (up to 17 ml/sample). At each time point (sample 1, Jun-Sept 2022; sample 2, Feb-Mar 2023; sample 3, Jul-Sept 2023) participants will be provided with either online (printable) or paper pathology collection forms to be presented at their local participating pathology laboratory. Informed consent for blood collection will be included with trial consent and obtained prior to enrolment.

Pathology laboratories will be instructed to label samples (with study identification number) and return (at ambient temperature) within 48 hrs to QIMR Berghofer sample processing unit. Once received, samples will be processed and stored in a -80°C freezer.

One serum aliquot will be used for estimation of serum 25(OH)D. Testing will be performed at the conclusion of the trial. While this will most likely occur at Metabolomics Australia, other companies may be offering this service at the time the testing is required, so we will investigate other options at that time.

To ensure the laboratory remains blinded, laboratory staff will not have access to the dataset containing participant allocation codes, and samples will be labelled with the participant identifier (as above) only.

10 Statistics

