10.1 Sample Size

We have based our sample size calculations on the ANCOVA analyses, considering the following factors:

- 1. A minimum difference in 25(OH)D concentration between treatment groups of 10 nmol/L; this is beyond the margin of assay error and a smaller difference is unlikely to be clinically relevant.
- 2. 90% power and 5% significance using a one-tailed test. A one-tailed test is appropriate because if sunscreen use increases 25(OH)D concentration this will not be of clinical or public health relevance (given the very high 25(OH)D needed before toxicity occurs).
- 3. Correlation between baseline and subsequent 25(OH)D values of 0.6 and standard deviation of 20 nmol/L: Based on a study in which 25(OH)D was measured on 333 participants from Brisbane and Canberra in all 4 seasons ([name], personal communication).
- 4. Non-compliance in the intervention group of 20%, and 10% uptake of daily sunscreen application in the control group.
- 5. Loss to follow-up of 20%.

The sample size required per group is 115. We require fully powered analyses within tertiles of ambient UVR and baseline 25(OH)D in order to devise appropriate public health and clinical messages. Thus the total sample size to be recruited is 345 per group (690 in total). With 552 participants (80%) completing the study the non-inferiority margin (90% power, α =0.05) is 4.5 nmol/L.

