10.3 Statistical Analysis Plan

Intention-to-treat analyses: Our main analyses will follow an intention-to-treat approach. 25(OH)D values in the Australian population are approximately normally distributed so we will model 25(OH)D as a continuous outcome using longitudinal analysis of covariance (ANCOVA). We will include treatment group (daily sunscreen or control), time, and the

interaction between treatment and time to estimate the difference in 25(OH)D concentration between treatment groups at the end of summer and at the end of winter. This method has been shown to reliably estimate the effect of treatment, accounting for any differences in the baseline value of the outcome measure.³³ All models will be adjusted for the variables used to stratify the randomisation and will include baseline 25(OH)D concentration as a covariate and participant as a random effect.

We will perform the analyses within the whole cohort and separately within tertiles defined according to: (1) average ambient UVR; and (2) baseline 25(OH)D concentration.

The incidence of skin lesions between the two groups will be assessed using Poisson regression.

Sensitivity analyses: To assess the effect of lack of compliance with the sunscreen intervention in the sunscreen group, and any routine sunscreen use in the control group, we will perform:

(a) An as-treated analysis using propensity score adjustment to minimise confounding. We will categorise sunscreen use into low (<30% of eligible days), moderate (30 to <70%), and high (\geq 70%). A generalised boosted model will be used to estimate the propensity score for sunscreen use, from which we will derive inverse probability of treatment weights. These will be used as weights in the ANCOVA models, both overall and within strata.

(b) Instrumental variable principal stratification to estimate the complier average causal effect, using the randomised allocation as the instrumental variable.³⁴ This method preserves the randomisation

Those in the intervention group will be classified as compliant if they used sunscreen on at least 70% of eligible days, and those in the control group will be classified as compliant if they used sunscreen on fewer than 20% of eligible days.

11 Responsibilities

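### Randomising single samples to assay batches gives up some precision that keeping each participant's three samples in one batch would retain at almost no cost

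*Protocol*

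**What the plan says.** Section 8.2.6 sets the batch rule: "samples will be randomly distributed across batches to avoid systematic differences between study groups or across time points". The same section says "All blood samples will be analysed at the end of the study", and section 9.6 says "Once received, samples will be processed and stored in a -80°C freezer". Each participant contributes three samples (baseline, end of summer, end of the following winter). Nothing in the protocol keeps the three together, and nothing expressly says that they are separated.

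Section 10.3 plans a longitudinal ANCOVA whose models "include baseline 25(OH)D concentration as a covariate and participant as a random effect". Section 10.1 bases the sample size on that analysis and lists "A minimum difference in 25(OH)D concentration between treatment groups of 10 nmol/L", "90% power and 5% significance using a one-tailed test" and "Correlation between baseline and subsequent 25(OH)D values of 0.6 and standard deviation of 20 nmol/L". The size is set so that analyses within tertiles of ambient UV radiation and of baseline 25(OH)D are fully powered. No between-batch CV is given, and the assay laboratory is not finally chosen.

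**The concern.** Because every sample is frozen and assayed after the trial, the sponsor is free to choose which samples share a batch. Randomising single samples prevents systematic differences between arms and time points, but with K batches of similar size two samples from one person share a batch only about one time in K. Their batch errors are then independent.

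Batch error enters the baseline and the outcome under either scheme. What changes is whether it is common to both. If it is, most of it cancels when the outcome is adjusted for baseline, and all of it cancels in a simple change score. If it is not, it weakens the baseline-to-follow-up correlation relative to what the same assay would give with co-batched samples. The precision at stake matters most in the tertile analyses, where the planned number is close to the bare requirement.

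**Working it through.** **Inputs from the protocol.** SD 20 nmol/L, correlation 0.6, difference 10 nmol/L, one-sided alpha 0.05, power 90%, non-compliance 20%, control uptake 10%, loss to follow-up 20% (section 10.1); population mean 25(OH)D 65 nmol/L (section 3.1).

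**Assumed, not in the protocol.** Between-batch CV of 3%, 5% or 8%, which at 65 nmol/L gives a between-batch SD s of 1.95, 3.25 or 5.2 nmol/L.

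**1. The plan's own figure.**
- Diluted difference: 10 × (1 − 0.20 − 0.10) = 7 nmol/L.
- ANCOVA residual variance: 400 × (1 − 0.6²) = 256 (SD 16).
- Completers per group: 2 × 256 × (1.645 + 1.282)² / 7² = 89.5, rounded up to 90.
- Recruited per group: 90 / 0.8 = 112.5, rounded up to 113, against 115 stated. The figure reproduces.
- Completers per arm in a tertile: 115 × 0.8 = 92. Power there without extra batch noise is 0.907.

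**2. Effect of batch error on the residual variance.** With slope 0.6 held fixed, batch error contributes (1 + 0.6²)s² = 1.36s² if the two samples are in different batches and (1 − 0.6)² s² = 0.16s² if they share one. More exactly, the residual variance is V − C²/V with V = 400 + s², where C = 240 if scattered and C = 240 + s² if together. This takes SD 20 and correlation 0.6 to exclude batch noise and applies no batch adjustment.

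| CV | s | Residual variance, scattered | Residual variance, together | Ratio | Tertile power, scattered | Tertile power, together |
|---|---|---|---|---|---|---|
| 3% | 1.95 | 261.2 | 256.6 | 1.02 | 0.902 | 0.906 |
| 5% | 3.25 | 270.3 | 257.6 | 1.05 | 0.893 | 0.905 |
| 8% | 5.2 | 292.2 | 260.1 | 1.12 | 0.871 | 0.903 |

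The power loss is 0.4, 1.2 and 3.2 percentage points. The number required per group (unrounded, after loss to follow-up) is 114 against 112, 118 against 113, and 128 against 114.

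**3. Whole cohort.** With 276 completers per arm, power for 7 nmol/L is above 99.9% without extra batch noise. At CV 8% scattered, the standard error is √292.2 × √(2/276) = 1.455; 7 / 1.455 − 1.645 = 3.17, so power is still about 99.9%.

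**4. Within-person change** (the secondary aim on determinants of change). Its variance is 2 × 400 × (1 − 0.6) = 320. Scattering adds 2s², that is 7.6, 21.1 or 54.1 (about 2%, 7% or 17%). One batch adds nothing.

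**5. If SD 20 and correlation 0.6 already contain independent batch noise.** The scattered scheme then simply has the planned residual variance of 256. Co-batching would lower it to 400 − (240 + s²)²/400 = 251.4, 243.0 or 221.7, and the number required per group from 112 to about 110, 106 or 97.

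**6. Effect of correcting for batch.** A simulation with 552 completers, batches of 90 samples (assumed) and a deliberately high CV of 10% (s = 6.5) gave a standard error for the arm difference of 1.53 scattered, 1.40 together, and 1.33 scattered after centring on batch means. The theoretical value with no batch noise is 16 × √(2/276) = 1.36. Within simulation error, the correction recovers the loss.

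**The case against.** The best case for the protocol is that its rule does what it sets out to do: no arm or time point is systematically tied to a batch. Splitting a participant's samples is inferred from the wording, not stated. The effect size rests on an assumed CV, and two statements point away from the high end: the assay is certified to a reference measurement procedure (section 8.2.6), and 10 nmol/L is described as larger than assay error (section 10.1). All of this stands, and it keeps the point small.

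Three stronger readings are tempting and are not supported:

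- A reader might infer that the tertile analyses will fall below 90% power. SD 20 and correlation 0.6 come from repeated measurements in 333 people and may already include assay noise. If so, scattering costs nothing against the plan.
- A reader might infer that section 10.3 is at fault for naming no batch term. Handling of assay batches is commonly left to the statistical analysis plan, which is not at hand and may contain one.
- A reader might infer that co-batching cleans the baseline value or the baseline tertiles. It does not; it only makes the batch error common to a participant's samples.

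What remains is that the allocation rule is fixed in the protocol, and a different rule meets the same aim with equal or better precision at almost no cost.

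**Conclusion.** The point holds as a minor, optional improvement in precision. There is no bias between arms and the whole-cohort comparison is not at risk. Relative to co-batching, and without batch adjustment, residual variance is about 2% to 12% higher and tertile power about 0.4 to 3 points lower for a between-batch CV of 3% to 8%. These figures rest on that assumed range, on a mean of 65 nmol/L, on the natural reading that single samples are scattered, and on planning inputs that exclude batch noise. If the planning inputs already contain it, the power losses against plan disappear and co-batching is purely a gain.

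**What to change.** Amend section 8.2.6 so that participants, not single samples, are randomised to batches, balanced by arm, with all of a participant's samples in the same batch and in random order within it. Each batch then holds the time points in equal numbers for participants with complete samples, so the section's stated aim is still met.

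The cost is a different pick list when samples leave the freezer. No extra assays are needed. Someone outside the laboratory who holds the allocation must prepare the balanced list; laboratory blinding is unaffected because tubes carry only the participant identifier. Version 7 is dated May 2023 and the last samples are due July to September 2023, so at that version the assays were still ahead.

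Adjusting for assay batch in the analysis is a useful complement. If the samples have to stay scattered, it would recover most of the loss by itself.

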9.1 Adverse Event Definitions

We will capture adverse events that are potentially related to the sunscreen application. These will be skin rashes, sunburn, falls, and fractures (with the latter potentially related to lowered 25(OH)D concentration).

9.2 Assessment of Severity

The severity of all AEs will be graded using the following criteria:

Severity	Description
Grade 1 (Mild)	Sign or symptom is present, but it is easily tolerated, is not expected to have a clinically significant effect on the participant's overall health and well-being, does not interfere with the participant's usual function, and is not likely to require medical attention.
Grade 2 (Moderate)	Sign or symptom causes interference with usual activity or affects clinical status, and may require medical intervention.
Grade 3 (Severe)	Sign or symptom is incapacitating or significantly affects clinical status and likely requires medical intervention and/or close follow-up.
Grade 4 (Life- threatening)	Sign or symptom results in a potential threat to life.
Grade 5 (Fatal)	Fatal Sign or symptom results in death

9.3 Assessment of Causality

Skin rash will be reported to the study physician who will assess causality. For other adverse events, causality cannot be determined during the course of the study. It is not possible to link any individual sunburn event to the intervention, and 25(OH)D will not be measured until the end of the study, so it will not be possible to assess causality of falls and fractures.

Relationship	Description
Unrelated	There is no evidence of any causal relationship
Possible	There is some evidence to suggest a causal relationship (e.g. because the event occurs shortly (within 24 hours) after administration of the trial medication). However, the influence of other factors may have contributed to the event (e.g. the participant's clinical condition, other concomitant treatments).

The assignment of causality for skin rashes will be based on the definitions below

Probable	There is evidence to suggest a causal relationship and the influence of other factors is unlikely.
Definite	There is clear evidence to suggest a causal relationship and other possible contributing factors can be ruled out.

9.4 Procedures for Recording and Reporting Adverse Events and Serious Adverse Events

- 1. Participants (or their families) may contact the study at any time after randomisation to let us know of an adverse event– they will be provided with a fridge magnet including the telephone number to facilitate this. These events will be recorded in the Sun-D database.
- 2. Each month participants will be asked to complete a short online survey in which they will be asked to report sunburn, falls, and fractures, including frequency, and severity.

Participants reporting skin rashes will be asked about symptom onset, with respect to sunscreen application, and about any other dietary or lifestyle changes that may have contributed. Participant reporting skin rashes will be offered Hamilton Sensitive sunscreen in place of Hamilton Active Family and/or Hamilton Everyday Face sunscreen and study staff will maintain regular contact with the participant to track symptoms. If a skin rash persists with use of Hamilton Sensitive and is assessed as being probably or definitely related to the study sunscreen, the participant will be withdrawn.

An adverse event report, capturing events reported in monthly surveys and by ad-hoc reporting, will be compiled monthly and provided to the TMG and the research office for review.

In the unlikely event that a participant experiences a skin rash that is possibly, probably or definitely related to the study medication, with severity ≥ 3 , the event will be reported to the sponsor within 24 hours of notification.

9.5 Clinical Laboratory Abnormalities

25(OH)D concentration will be measured at the end of the study. Participants will be notified of their results, and advised that if the concentration in any of the 3 samples was < 50 nmol/L they should discuss this with their regular doctor.

9.6 Laboratory Specimen Preparation, Handling, Storage and Shipment

Each participant will be asked to provide 3 blood samples (up to 17 ml/sample). At each time point (sample 1, Jun-Sept 2022; sample 2, Feb-Mar 2023; sample 3, Jul-Sept 2023) participants will be provided with either online (printable) or paper pathology collection forms to be presented at their local participating pathology laboratory. Informed consent for blood collection will be included with trial consent and obtained prior to enrolment.

Pathology laboratories will be instructed to label samples (with study identification number) and return (at ambient temperature) within 48 hrs to QIMR Berghofer sample processing unit. Once received, samples will be processed and stored in a -80°C freezer.

One serum aliquot will be used for estimation of serum 25(OH)D. Testing will be performed at the conclusion of the trial. While this will most likely occur at Metabolomics Australia, other companies may be offering this service at the time the testing is required, so we will investigate other options at that time.

To ensure the laboratory remains blinded, laboratory staff will not have access to the dataset containing participant allocation codes, and samples will be labelled with the participant identifier (as above) only.

10 Statistics

10.1 Sample Size

We have based our sample size calculations on the ANCOVA analyses, considering the following factors:

- 1. A minimum difference in 25(OH)D concentration between treatment groups of 10 nmol/L; this is beyond the margin of assay error and a smaller difference is unlikely to be clinically relevant.
- 2. 90% power and 5% significance using a one-tailed test. A one-tailed test is appropriate because if sunscreen use increases 25(OH)D concentration this will not be of clinical or public health relevance (given the very high 25(OH)D needed before toxicity occurs).
- 3. Correlation between baseline and subsequent 25(OH)D values of 0.6 and standard deviation of 20 nmol/L: Based on a study in which 25(OH)D was measured on 333 participants from Brisbane and Canberra in all 4 seasons ([name], personal communication).
- 4. Non-compliance in the intervention group of 20%, and 10% uptake of daily sunscreen application in the control group.
- 5. Loss to follow-up of 20%.

The sample size required per group is 115. We require fully powered analyses within tertiles of ambient UVR and baseline 25(OH)D in order to devise appropriate public health and clinical messages. Thus the total sample size to be recruited is 345 per group (690 in total). With 552 participants (80%) completing the study the non-inferiority margin (90% power, α =0.05) is 4.5 nmol/L.

10.2 Analysis Objectives and Endpoints

The **primary aim** is to determine whether participants randomised to provision of a broadspectrum SPF 50+ sunscreen, and advice to apply it to all body parts uncovered by clothing on all days when the UVI is forecast to reach 3, have a lower mean 25(OH)D concentration at the end of either summer or winter than those randomised to usual discretionary sunscreen use.

Secondary aims are to:

- a. Determine whether the intervention affects 25(OH)D concentration at the end of winter or summer within tertiles of:
 - i. Erythemally weighted ambient UV radiation at the postcode of usual residence
 - ii. Baseline 25(OH)D concentration
- b. Identify environmental and participant factors that influence the change in 25(OH)D concentration in sunscreen users.
- c. Assess the effect of frequent sunscreen application on malignant and pre-malignant skin lesions during the study and over the following 2 years.

10.3 Statistical Analysis Plan

Intention-to-treat analyses: Our main analyses will follow an intention-to-treat approach. 25(OH)D values in the Australian population are approximately normally distributed so we will model 25(OH)D as a continuous outcome using longitudinal analysis of covariance (ANCOVA). We will include treatment group (daily sunscreen or control), time, and the

interaction between treatment and time to estimate the difference in 25(OH)D concentration between treatment groups at the end of summer and at the end of winter. This method has been shown to reliably estimate the effect of treatment, accounting for any differences in the baseline value of the outcome measure.³³ All models will be adjusted for the variables used to stratify the randomisation and will include baseline 25(OH)D concentration as a covariate and participant as a random effect.

We will perform the analyses within the whole cohort and separately within tertiles defined according to: (1) average ambient UVR; and (2) baseline 25(OH)D concentration.

The incidence of skin lesions between the two groups will be assessed using Poisson regression.

Sensitivity analyses: To assess the effect of lack of compliance with the sunscreen intervention in the sunscreen group, and any routine sunscreen use in the control group, we will perform:

(a) An as-treated analysis using propensity score adjustment to minimise confounding. We will categorise sunscreen use into low (<30% of eligible days), moderate (30 to <70%), and high (\geq 70%). A generalised boosted model will be used to estimate the propensity score for sunscreen use, from which we will derive inverse probability of treatment weights. These will be used as weights in the ANCOVA models, both overall and within strata.

(b) Instrumental variable principal stratification to estimate the complier average causal effect, using the randomised allocation as the instrumental variable.³⁴ This method preserves the randomisation

Those in the intervention group will be classified as compliant if they used sunscreen on at least 70% of eligible days, and those in the control group will be classified as compliant if they used sunscreen on fewer than 20% of eligible days.

11 Responsibilities

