CONFIDENTIAL

Clinical Trial Protocol

The Sun-D Trial

PROTOCOL NUMBER: P3755

Version:7 Date: 25 May 2023

SPONSOR

QIMR Berghofer Medical Research Institute [name]

PRINCIPAL INVESTIGATOR

[name] QIMR Berghofer Medical Research Institute [name] [contact]

CONFIDENTIALITY STATEMENT: This document contains information that is privileged or confidential. As such, it may not be disclosed unless specific prior permission is granted in writing by QIMR Berghofer or such disclosure is required by federal or other laws or regulations. Persons to whom any of this information is to be disclosed must first be informed that the information is confidential. These restrictions on disclosure will apply equally to all future information supplied, which is indicated as privileged or confidential.

PROTOCOL AMENDMENT HISTORY

Protocol Version Number	Protocol Version Date	Primary Reason for Amendment						
2	8/02/2022	 Specify inclusion of ACT (Section 5.1 & 7.1) Specify interview format (Section 6.1) Addition of independent TMG member (Section 11.2.2 and appendix 1) 						
3	16/05/2022	 Specify use of third party databases and mailing lists in recruitment activities (section 6.1) Removal of Coles Myer specification for gift vouchers. (section 6.1) 						
4	29/06/2022	 Eligibility age range amended to include 18-<30 and 65-70 year olds. Further specification of mailing lists to be used for recruitment (section 6.1) 						
5	12/07/2022	 Increased compensation for blood collection and removed 1 person per household limit (section 6.1) Specified allergy exclusion criteria (section 6.4) 						
6	14/03/2023	1. Addition of Hamilton Sensitive sunscreen (sections 7.3, 7.5, 7.7 & 9.4)						
7	25/05/2023	 End of study definition updated (Section 5.4) Retention point 5 updated to tri-monthly (section 6.1) AE updated to bring in line with changes made in protocol version 6 (Section 7.10.1) Inclusion of final survey (section 8.2.3) 						

PROTOCOL SYNOPSIS

Full Title:	The Sun-D Trial: the effect of high SPF sunscreen application on vitamin D							
Short Title:	The Sun-D Trial							
Project Number:	P3755							
Objectives:	Primary: To determine whether routine application of high SPF sunscreen on all days when the ultraviolet (UV) index is forecast to be \geq 3 leads to a decrease in 25 hydroxy vitamin D (25(OH)D) concentration.							
	econdary:							

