5.1 Overall Study Design

Phase: Phase 4 RCT to determine effect of sunscreen application on serum 25(OH)D concentration.

Randomisation: Randomised computer-generated randomisation in a 1:1 ratio, stratified using permuted blocks by state of residence (QLD; NSW/ACT; VIC; TAS), age (18-44; 45-70), and sex. We will use cluster randomisation to ensure participants from the same household are randomised to the same study arm.

Control: Standard Cancer Council information to protect the skin when outdoors for more than a few minutes when the UV Index is \geq 3, provided at baseline.

Blinding: Open label. Blood samples and data will be analysed blinded to study group.

Rationale: An RCT is needed to determine the effect of regular sunscreen application, as observational studies are frequently confounded by indication. It would be unethical to use a placebo sunscreen. We will recruit people who are not already using sunscreen routinely to avoid contamination in the control group, and advise that we want them to continue their usual behaviour during the course of the trial.

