6.1 Participant Recruitment and Retention Strategies

Participants will be recruited primarily from the Australian Electoral Roll. We will also enable volunteer recruitment, through use of third party databases and mailing lists such as the Join Us Register and university mailing lists (pending necessary approvals from each organisation), supported by traditional and social media. Participants enrolled in other QIMR Berghofer-sponsored studies (e.g., QSkin, the D-Health Trial), or who have subscribed to QIMR mailing lists, will be advised of the opportunity for them or their family/friends to participate, with HREC approval for the relevant study.

Recruitment approach

- 1. Invitation letter, including an eligibility questionnaire to conduct an initial eligibility screen (completed on paper or online). Volunteers will be able to access the eligibility questionnaire through a publicly available link.
- 2. Phone call to people who are eligible on the eligibility questionnaire to confirm eligibility criteria.
- 3. Email link to participant information sheet, consent form, questionnaire.
- 4. Email/mail pathology request form (according to participant preference).
- 5. Randomisation after consent form, questionnaire, and blood sample received.

Retention strategies

All participants:

- 1. Will receive a \$50 e-voucher card for each sample returned to QIMR Berghofer, as compensation for their time;
- 2. Will be informed of all 25(OH)D test results at the end of the study

Intervention group only:

- 1. Will receive weekly reminders, including information about the forecast UVI
- 2. Be invited to a closed Facebook group providing access to videos, hints about sunscreen application, sunscreen and sun exposure facts etc.
- 3. Regular email updates about study progress, including short videos to encourage application
- 4. Advice about how to download and use the SunSmart App which displays the daily forecast UVI for their location.
- 5. After the first two weeks and then tri-monthly we will contact participants in the intervention group to identify barriers to sunscreen use and to suggest solutions. Interviews will be conducted over Zoom or by telephone, and recorded, with consent from the

participant at the time of contact. At enrolment participants will be asked to nominate their preferred contact mode including preference for video or non-video call.

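### Households are randomised as clusters, but the planned ANCOVA models carry only a participant random effect; if co-residents enrol and their outcomes correlate, standard errors are somewhat too small

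*Protocol*

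**What the plan says.** On allocation, section 5.1 of the protocol states: "We will use cluster randomisation to ensure participants from the same household are randomised to the same study arm". The amendment history records that version 5 removed the limit of one person per household, and the current section 6.1 contains no such limit. Section 6.1 also says that people in other studies of the institute, or on its mailing lists, "will be advised of the opportunity for them or their family/friends to participate".

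On analysis, section 10.3 models 25(OH)D with a longitudinal ANCOVA containing treatment, time and their interaction. It adds: "All models will be adjusted for the variables used to stratify the randomisation". Those variables are state, age group and sex. The models will also "include baseline 25(OH)D concentration as a covariate and participant as a random effect". The same analyses are to be run in the whole cohort and within tertiles of ambient UVR and of baseline 25(OH)D.

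On sample size, section 10.1 lists five factors, including "90% power and 5% significance using a one-tailed test" and "A minimum difference in 25(OH)D concentration between treatment groups of 10 nmol/L". None of them concerns households.

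**The concern.** When people are allocated together, the variance of the treatment contrast includes the covariance between them. A participant random effect accounts for two follow-up values from one person. It does not account for two people who were given the same arm because they live together.

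Co-residents share a location and ambient UV and may share habits, so some positive correlation is plausible after adjustment for baseline 25(OH)D, state, age and sex. A model that ignores it gives standard errors that are too small, intervals that are too narrow and a one-sided test that rejects too often. At stake are the type I error of the primary comparison and the claim in section 10.1 that the tertile analyses are fully powered. Co-residents share a postcode and so normally fall in the same ambient-UVR tertile, which means that the clustering carries into those analyses.

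**Working it through.** **Reproducing the plan's figure.** Inputs from section 10.1: difference 10 nmol/L, SD 20, baseline correlation 0.6, one-sided 5%, 90% power, 20% non-compliance, 10% control uptake, 20% loss.

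- Diluted effect: 10 × (1 − 0.2 − 0.1) = 7 nmol/L.
- ANCOVA SD: 20 × √(1 − 0.6²) = 16 nmol/L.
- Completers per group: 2 × (1.645 + 1.282)² × 16² / 7², which rounds up to 90.
- With 20% loss: 90 / 0.8 = 112.5, so 113, against the stated 115.

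The stated figure is matched within two participants with no design effect, so section 10.1 leaves no room for clustering.

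**Effect of ignoring households.** Suppose that a share f of participants belong to two-person households and that residual 25(OH)D within a household has correlation ICC. The protocol gives neither value; both are assumptions.

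- Design effect: DE = 1 + f × ICC.
- Ratio of true to model standard error: √DE.
- True size of the nominal one-sided 5% test: 1 − Φ(1.645 / √DE).
- Tertile power, with 115 × 0.8 = 92 completers per arm: Φ(7 / (16 × √(2 × DE / 92)) − 1.645).

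| f | ICC | DE | SE ratio | True size | Tertile power |
|---|---|---|---|---|---|
| any | 0 | 1.00 | 1.000 | 0.0500 | 0.907 |
| 0.1 | 0.2 | 1.02 | 1.010 | 0.0517 | 0.902 |
| 0.1 | 0.3 | 1.03 | 1.015 | 0.0525 | 0.8995 |
| 0.2 | 0.2 | 1.04 | 1.020 | 0.0534 | 0.897 |
| 0.2 | 0.3 | 1.06 | 1.030 | 0.0551 | 0.892 |
| 0.4 | 0.5 | 1.20 | 1.095 | 0.0666 | 0.856 |

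**Whole cohort.** With 345 × 0.8 = 276 completers per arm, power for 7 nmol/L is 0.9998 at DE 1 and 0.9988 at DE 1.20.

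**Refining the tertile figures.** The table applies the full f to completers. If losses are independent, a completer's partner is retained 80% of the time.

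- Ambient-UVR tertiles, upper case: DE = 1 + 0.4 × 0.8 × 0.5 = 1.16, power about 86.7%.
- Baseline-25(OH)D tertiles, upper case: partners may fall in different tertiles. If their baseline values correlate at 0.5 (a further assumption, bivariate normal), they share a tertile about 49% of the time. Then DE = 1 + 0.4 × 0.8 × 0.49 × 0.5 ≈ 1.08, with size about 5.7% and power about 88.7%.

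**Check by simulation.** A participant-level ANCOVA was simulated with 552 completers, two-person households and no treatment effect, 4,000 runs per setting (Monte Carlo standard error √(0.05 × 0.95 / 4000) ≈ 0.003).

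| f | ICC | Rejection, participant-level SE | Rejection, household-robust SE |
|---|---|---|---|
| 0.1 | 0.3 | 0.048 | 0.047 |
| 0.2 | 0.3 | 0.055 | 0.050 |
| 0.5 | 0.5 | 0.078 | 0.056 |

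At the smallest setting the inflation cannot be told from noise. At the largest it is clear, and household-robust errors remove most of it.

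**The case against.** The strongest reply is that the effect may be negligible. Recruitment is primarily from the electoral roll, and every co-resident must separately meet the entry criteria. The protocol permits co-enrolment but does not say that it is common. Baseline 25(OH)D is a covariate and will absorb part of what co-residents share, so the residual ICC may be low. If no household has two participants, or the residual ICC is zero, nothing changes. All of this stands, and it limits the size of the point. It does not remove the mismatch between how people are allocated and how they are analysed.

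A second reply is that variance details belong in a statistical analysis plan, which may exist. For the ANCOVA models this does not succeed, because section 10.3 itself states the random-effect structure. For the Poisson analysis of skin lesions and the complier average causal effect it does succeed: section 10.3 is silent on their variance, and a reader who infers that they assume independence goes beyond the text.

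Two other inferences are not supported. The family and friends wording in section 6.1 concerns people in the institute's other studies or on its mailing lists, so it does not show that Sun-D participants are asked to bring in household members. And although section 10.1 quotes a non-inferiority margin, section 10.3 defines no non-inferiority test to which the error could be applied.

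**Conclusion.** The point holds conditionally. As written, the primary and tertile ANCOVA models ignore the unit of randomisation for any household with more than one participant, and the sample size does too. The direction of error is clear if residual household correlation is positive.

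Under modest assumptions (f 0.1 to 0.2, ICC 0.2 to 0.3) the standard error is understated by 1% to 3%, and ambient-UVR tertile power stays at about 89% to 90%. In the upper case (f 0.4, ICC 0.5) that tertile power is about 86% to 87%. Baseline-25(OH)D tertiles suffer less.

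A reader might conclude that the trial's p-values are certainly too small, or that the primary result is in jeopardy. The protocol does not support either reading: it gives no household counts or ICC, and whole-cohort power exceeds 99% throughout the range. Severity is moderate to minor; this is not a must-fix defect.

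**What to change.** In section 10.3, specify household-clustered robust standard errors for the primary and tertile ANCOVA models. A household random intercept with participant nested within it is an alternative if it can be estimated; with mostly single-participant households the two variances may be hard to separate, so the robust option is the safer default. State that the weighted, complier average causal effect and skin-lesion analyses will use the same clustering, and report the number and size of households with more than one participant.

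In section 10.1, say that the sample size ignores household clustering.

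Settle this before the unblinded analysis. It needs only household identifiers and a small change to wording and code. The price is slightly wider intervals.
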